Protocol No: EGG01 ; Version: 1.0 ; dt: 09 Jul 2022

STUDY PROTOCOL

Study Title: **GASTRIC MYOELECTRICAL ACTIVITY WITH WATER LOAD SATIETY TEST AS A PREDICTOR OF INDIVIDUAL SUCCESSFUL RESPONSE TO TREATMENT BY VARIOUS BARIATRIC PROCEDURES**

Promoted by GETTEMO-SEED

Director of the Study: [name]

Coordinator of the Study: [name]

Protocol No:

Product Name: NA

Type of Study: Investigator Initiated study

Date: June 25, 2022

Principal Investigator: [name]

Consultant Gastroenterologist & Therapeutic Endoscopist,

Director - Endoscopy (Center for Obesity & Metabolic Therapy)

Email: [contact]

Summary

Background: Total body weight loss (TBWL) after Bariatric Endoscopy (BE) is variable. Gastric emptying may be normal, rapid or delayed in patients with obesity and be a factor in variable BE outcomes. Gastric myoelectrical activity (GMA) reflects gastric pacemaker activity which controls gastric contractions. The non-invasive electrogastrogram (EGG) uses standard electrodes positioned on the abdominal surface to record GMA. There is currently a lack of studies in a population with obesity utilizing EGG to determine GMA patterns. We postulate that GMA patterns recorded with EGG will reflect subgroups in regards to stomach electrical physiology in obesity and that these subgroups will be useful in selecting patients for various BE procedures to maximize success of the procedures.

Hypothesis: We postulate that GMA patterns recorded with Pre-intervention EGG can predict clinical success and adverse events after bariatric interventions.

1.- INTRODUCTION

1.1. Severe obesity as a health problem

Obesity, defined as a body mass index (BMI) of 30 kg/m², is increasing worldwide at alarming rates and is a cause of comorbidity and death. Nearly 2.8 million people die each year from obesity and being overweight according to the World Health *Organization*. In developed countries, the prevalence is more than 25%, with a high load of chronic comorbidities (hypertension, diabetes, atherogenic dyslipidemia, sleep apnea syndrome, hepatic steatosis, osteoarthritis, cancer, etc. (1).

In Europe it is known by the European Association for the Study of Obesity (EASO) that, in the last decade, in countries such as Spain 30% of its children population (7-11 years) was obese and that there was, respectively, a prevalence of overweight of more than 39% and 15% in adults between 25 and 60 years. This year the prevalence of overweight could amount to > 70% of the population and that of obesity, to > 40 and it is worst after the lockdown because of covid-19 pandemic. Adulthood obesity prevalence forecasts (2010–2030) predict that in 2020, 27% of men and 19% of women will be obese. By 2030, the model predicts that 36% of men and 21% of women will be obese (1). In addition, it is severe and morbid obesity that grows proportionately the most (with prevalence > 5-10 % of the population) and the costs of this disease have a cost of almost 10% of the total health budget in the European Union. Thus, the socio-health impact is greater since medical treatments, based on lifestyle changes, are less effective. In this scenario, bariatric techniques (endoscopic or surgical), at present is the only effective long-term treatment that can offer significant weight loss (> 15-20%) and a parallel reduction in associated comorbidities (2).

More than 135 million individuals are obese in India. The prevalence of obesity and central obesity varies from 11.8% to 31.3% and 16.9% to 36.3% respectively.(36) The prevalence of obesity is higher among the urban population, higher socioeconomic status, and south India.(35)

In addition to preventing the development of obesity it is necessary to individualize therapies for each obese patient by selecting the most appropriate BE treatment, based on

gastric physiology as described below, in order to increase the likelihood of successful total body weight loss (TBWL) and maintenance.

1.2. Bariatric Techniques:-

Bariatric techniques can be divided into three categories: restrictive, malabsorptive and mixed. In the first one, the procedures can be surgical or endoscopic. Malabsorptive techniques act on gastric capacity and perform complex anatomical short circuits that aim to reduce body weight significantly in very obese patients (BMI < 45 kg/m²), at the expense of producing a "controlled malabsorption" picture of nutrients, vitamins and minerals. Gastric bypass has been the "gold-standard" technique in bariatric surgery for decades, due to its long-term efficacy and it combines a restrictive procedure with another maldigestive, allowing average weight loss of around 30%, without side effects of intestinal malabsorption.

As a restrictive bariatric surgery technique, sleeve gastrectomy is the procedure of choice today, which due to its relatively low technical difficulty and results close to those of gastric bypass, is displacing other surgical techniques at the international level. worldwide Technically, a gastric tubular reservoir is created guided by a Fouchet orogastric tube calibrated at 42 Fr (14 mm), sectioning the greater gastric curvature from 6 cm proximal to the pylorus to the bottom. In this way the gastric volume is reduced by approximately 70-80%. This technique allows full maintenance of gastric functions, gastric emptying through the pylorus and without the need to act on the absorption of nutrients at the intestinal level.

According to 2019 data from the International Federation for the Surgery of Obesity (IFSO), SG is the preferred technique used in Europe (43%), compared to gastric bypass (35%), which came in second place. In Spain, gastric bypass continues to occupy first place (43%), compared to GV (34%), followed by biliopancreatic diversions (13.6%), mini-gastric bypass (6.2%), gastric band adjustable (1.1%) and gastric plication (0.9%). As for India in the year 2014, the percentage distribution of different procedures performed was 68% for LSG, 16% for LRYGB, and 14% for MGB-OAGB. In 2018, 48% of the procedures performed were LSG, while MGB-OAGB and LRYGB were at 34% and 15%, respectively.(37)

Bariatric endoscopy (BE) techniques have emerged as safe and effective treatment that include restrictive endoscopic techniques: Intra-gastric balloons (IGB), endoscopic sleeve gastropasty (ESG), primary surgery obesity endoluminal (POSE) or Endo-Sleeve (GESP or POSE 2.0) procedures; malabsorptive techniques: endoluminal bypass (endobarrier), duodenal mucosa resurfacing; extraction methods (Aspire); electrical stimulation: gastric pacemaker, vagal blockage and other procedures including botulinum toxin, magnetic compression anastomosis or the novel endozip (2, 3, 4,5,6).

1.3. Gastric motility, electrogastrigraphy, weight control and bariatric techniques

Total body weight loss (TBWL) in response to these therapies is variable. The pathophysiological mechanisms involved behind bariatric techniques go beyond restrictive capacity and malabsorption secondary to anatomical changes caused by different therapeutic procedures that help explain the improvement of metabolic disorders (diabetes, insulin resistance, dyslipidemia, improvement of hepatic steatosis, etc.). even before weight loss has been clearly evident with changes in the secretion and regulation profile of gastrointestinal hormones, bile acids, pro-inflammatory cytokine pattern, immune capacity, intestinal microbiota, etc (7).

The combination of hormonal and gastric electrophysiological changes due to weight loss has physiological significance in light of the association between obesity and accelerated gastric emptying (GE) and the fact that GE delay of solids is an important determinant of fullness and satiety in humans (8).

The stomach is a complex neuromuscular organ that receives, mixes and empties ingested food. The neuromuscular work of the stomach is coordinated by the gastric pacemaker which controls the frequency and propagation of gastric peristaltic waves. For normal emptying of liquids and solids from the stomach into the duodenum integrated coordination of corpus-antral-pyloric contractions are required.

There are neurogenic factors (parasympathetic afferents -efferents, intrinsic gastric pacemaker function), hormonal and biochemical factors (cholecystite, gamma-aminobutyric acid, ghrelin, etc.), all of which have feedback mechanisms that affect gastric motility. There are also anatomical factors such as structural alterations or inflammatory conditions that affect motility and here is remarkable the role of interstitial cells of Cajal (ICCs). ICCs are the pacemaker cells and interface between enteric nerves and smooth muscle cells and the key to gastric motility. ICCs create the rhythmic 3 cpm electrical conduction system that coordinates the three per minute gastric peristaltic waves that results in normal gastric emptying (9).

Variable weight loss and intolerance of BE procedures are appreciated. For this protocol we define Failure of BE methods when patient only obtain less than 25% of EWL after 6 months of BE, according to the Part 1 of the BAROS (Bariatric Analysis and Reporting Outcome System) scale adapted to endoscopic treatment (2) (Table 1).

After BIG placement, patients present intolerance such vomit and abdominal pain in 70-90% of cases at the first week but these effects can be extended up to three weeks (18%) and removal of the balloon in 4% of patients (3). Gastric emptying measured by gastric scintigraphy breath test or stable isotope breath tests show that there are physiological predictors of intolerance and response to BIG placement (10). Many studies show that patients after ESG at 6 months achieved a mean of 50% of EWL or more with rate of severe adverse events around 2% , including pain or nausea requiring hospitalization, upper gastrointestinal bleeding and peri-gastric leak or fluid collection (11).

After SEG.....

.....

Table 1 . BAROS (BARIATRIC ANALYSIS AND REPORTING OUTCOME SYSTEM) ADAPTED TO BARIATRIC ENDOSCOPY

1. Percentage of excess weight loss (%EWL): (Initial weight – Current weight) / (Initial weight – Ideal weight) × 100 (-1): Weight gain (0): Weight loss 0-24% (+1): Weight loss 25-49% (+2): Weight loss 50-74% (+3): Weight loss > 75%
 
2. Comorbidity: (-1): Aggravated (0): Unchanged (+1): Improved (unresolved) (+2): Improved: one major resolved, others improved (+3): Improved: all majors resolved, others improved
 
3. Quality of life questionnaire: (much worse, worse, unchanged, better, much better) Self-esteem (scale -1, -0.5, 0, +0.5, +1) Physical (scale -0.5, -0.25, 0, +0.25, +0.5) Social (scale -0.5, -0.25, 0, +0.25, +0.5) Work (scale -0.5, -0.25, 0, +0.25, +0.5) Sex (scale -0.5, -0.25, 0, +0.25, +0.5)
 
4. Complications: (-0.2): Per minor complication (-1): Per major complication (-1): In case of repeat endoscopy or surgery
	
Final score (sum total of above 4 items)
 
• No comorbidities: Failure: 0 or less Fair: 0-1.5 Good: 1.5-3 Very good: 3-4.5 Excellent: 4.5-6• Comorbidities: Failure: < 1 Fair: 1-3 Good: 3-5 Very good: 5-7 Excellent: 7-9
--	--

Thus, a fuller understanding of gastric physiology before undertaking BE treatments may lead to better patient selection for each procedure.

An important aspect of gastric emptying and physiology is GMA which reflects the gastric pacemaker activity that coordinates gastric peristaltic contractions. The GMA is measured with electrogastrography methods that will be used in this study.

Electrogastrography is a non-invasive method of recording GMA that is used to diagnose gastric dysrhythmias in patients with intractable chronic nausea and vomiting, gastroparesis and gastroesophageal reflux (15,16,17). Electrogastrography signals are recorded using standard EKG-type electrodes placed on the surface of the upper stomach. 3CPM Company developed the first patented, non-invasive FDA-approved diagnostic device that records and displays the EGG signal and provides analysis of the GMA signal for clinical diagnosis.

Gastric dysrhythmias (tachygastria, 3.7 to 10 cpm, bradygastria, 1.0-2.5 cpm) and mixed dysrhythmias (combinations of tachygastria and bradygastria) are recorded with electrogastrography (17,18,19). In addition, patients with gastroparesis may have normal (2.5 to 3.7 cpm) or hypernormal GMA. These patients have antro-pyloro-duodenal

outflow dysfunction and respond well to endoscopic or surgical therapies (20). The pattern(s) of GMA in response to the WLST in obese patients who will undergo BE procedures is unknown. In addition, the volume of water ingested in 5 minutes during the WLST indicates gastric capacity or accommodation which may be an important variable in patient selection for BE. Finally, in patients with functional dyspepsia or gastroparesis, symptoms induced by the WLST include nausea, fullness, bloating and pain and are scored on a VAS. These symptoms, if elicited in the obese patients, may also represent an important variable for patient selection (21, 22, 23).

The position of the electrodes on the upper abdominal surface, skin preparation and test meals influence the GMA recordings. Interestingly, neither age nor sex has a definitive impact on the parameters for in adults or children (24, 25, 26).

Controversial findings on the correlation between EGG and GE have been reported in the literature. Different authors have said that a normal 3 cpm GMA may not predict normal GE and dysrhythmic GMA may be present in delayed GE but is also present in functional dyspepsia. Patients with delayed GE and abnormal EGG have more severe symptoms and more tachygastria in pre and post-prandial states than patients with normal GE. 80% of the non-obese population has normal EGG and 20% have variability (27, 28, 29, 30). There is only one preliminary study of GMA with WLST before BE techniques in obesity (31), but has not been studied in before and after BE procedures to determine subtypes of GMA and whether or not subtypes will predict successful bariatric outcomes.

Therefore, we propose a study to evaluate the GMA in response to the WLST in patients who have agreed to BE procedures. We hypothesize that GMA patterns in response to the WLST, the volume of water ingested and the array of symptoms elicited will help to predict successful outcomes of the bariatric procedures and thus help with patient selection for these procedures.

2.- WORKING HYPOTHESIS

Weight loss and long-term maintenance may be conditioned by changes in GMA, as well as by anatomical modifications induced by the bariatric procedure.

Since anatomical modifications of the stomach by the BE procedures are related to weight loss, our purpose is to determine whether different procedures to reduce gastric capacity will result in substantial changes in GMA and in the water load volume ingested. No studies that have studied obese population before and after such BE procedures are available.

Therefore, an important question is whether obese patients have the GMA that is similar to those with functional dyspepsia and normal weight (32). Also, the usefulness of electrogastrography as a new tool to customize choice of Bariatric therapies by determining success or failure based on GMA and WLST results has not been studied. GMA measures the normal or depleted gastric ICCs and the WLST measures gastric capacity, objective measures that may be important to predict success of Bariatric procedures and thus to help with patient selection to maximize efficacy and minimize side effects (32).

Hypothesis Question: Pre-intervention EGG can predict clinical success and adverse events after bariatric interventions?.

Demonstrate the usefulness of EGG measuring the GMA by identifying subtypes with the Water Load Satiety Test (WLST) in obese adults to predict individual successful responses to BE treatments: Intra-gastric Balloon (IGB) placement and Apollo Endoscopic Sleeve Gastroplasty (ESG) method.

Demonstrate the usefulness of EGG measuring the GMA by identifying subtypes with the Water Load Satiety Test (WLST) in obese adults to predict individual successful responses to BE treatments: Intra-gastric Balloon (IGB) placement and Apollo Endoscopic Sleeve Gastroplasty (ESG) method

3.- OBJECTIVES

3.1.- Primary Objective –

- . Pre-intervention EGG parameters and/or changes in EGG parameters (one/three months) after bariatric intervention can predict clinical success at the end of follow up
- a. Pre-intervention EGG parameters and/or changes in EGG parameters after the bariatric intervention can predict adverse events at the end of follow-up.

3.2. Secondary:

- a. Secondary Objective
To predict suitable bariatric intervention for patients depending upon a pre-intervention EGG.
- b. EGG is a feasible diagnostic tool in obese population with reproducible and predictable results

4.- STUDY DESIGN AND METHODOLOGY

4.1. Type of study: Multicenter, prospective, observational study in patients with body mass index (BMI) at 30 kg/m² prior and after one, and three, six and 12 months of a bariatric procedure. All tests will be analyzed by one blinded specialist.

4.2. Study design: This is a pilot study, involving 2 hospitals in Spain and India, where 4 groups of patients will be recruited.

- a) Group of 50 patients who will undergo BIG placement
- b) Group of 50 patients who will undergo Endoscopic Sleeve Gastroplasty (ESG) Apollo method.
- c) Group of 50 patients who will undergo Surgical Sleeve Gastrectomy (SEG) Apollo method

d) Group of 50 patients who will undergo RYGB method

The protocol will be carried out in the run-up to the BE procedure until 12 months after of follow up. As a control group, 50 people (of the same age and gender) will be selected, with BMI less than 25% who voluntarily agree to participate in the protocol and have the same criteria of inclusion or exclusion of patients that belongs to all the groups, except BMI.

Duration – 18 months to 24 months

4.3. Characteristics of subjects:

Voluntary patients with obesity will be recruited among those patients who will be given any of the four types of bariatric procedures described above, at the time before and after the first, third, sixth and 12 months of performing the bariatric methods.

Patients will be recruited in AIG Hospitals, Gachibowli, Hyderabad

Inclusion criteria:

1. Men and women, aged between 18-65 yrs
2. IMC basal ≥ 30 kg/m²
3. Patient undergoing bariatric intervention willing to participate in the study
4. Informed consent (oral and written) for the tests to be carried out.

Exclusion criteria:

1. Presence of severe cardiac, renal, hepatic, or neurological disease
2. Long term use of medication that alter gastric motility (> 4 weeks)
3. Significant alcohol or opioids or narcotics or tobacco
4. Active malignancy
5. Pregnancy
6. Uncontrolled Diabetes Mellitus with glycosylated hemoglobin (HbA1c) levels $\geq 6.5\%$ or glucose level more than 270 mg/dL.
7. Uncontrolled hypothyroidism (High TSH with low levels of Free T4)

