****The total volume of water consumed will be recorded.***

4.7. EGG signal analysis

EGG signal is reviewed for movement artifacts. Artifact – free minutes are chosen for blinded computer analysis (at baseline, three, six and 12 months recordings and for each type of BE procedure). The selected minutes of EGG are analyzed by spectral analysis

by computer applications. 3CPM EGGSAS GMAT Threshold software will be used for signal analysis. EGG data will be organized by clinical diagnosis. Water load volumes ingested that are <238 ml are considered abnormally low (33).

5.- STATISTIC

The normal distribution of the variables will be confirmed by the kolmogorov-Smirnoff test. Quantitative variables shall be expressed as mean s/e d or means (interquartile range). Comparison between groups will be performed by parametric or nonparametric tests, depending on the distribution of the variables. Spearman or Pearson correlation will be used for the study of correlations. The possibility of multivariate logistic regression analysis will be explored. An SPSS statistical programme will be used. EGG data will be descriptive in terms of overall clinical EGG diagnosis and normal or abnormal water load volume ingested. Symptom data before and after the WLST will be tabulated. These measures will be calculated before and 3 and 6 months after the BE procedures.

6.- STUDY LIMITATIONS

Recruitment of the number of subjects should not be a problem due to the high number of patients performed in the different centers and will allow the selection of those with the most approximate clinical results between groups.

A strength of the study is to have a control group of non-obese subjects, which will allow us to know the normal pattern of GMA in response to the WLST and whether it is similar to those worldwide reported in healthy individuals.

All tests will be carried out by the same expert operator in the medical center and analyzed by one specialist in EGG that received the blinded information from all the centers because it is a multicenter study, but the bariatric procedures will be performed by different operators from every center.

7.- STAGES OF DEVELOPMENT AND DISTRIBUTION OF THE AREAS OF ALL RESEARCH EQUIPMENT

The clinical study will be conducted simultaneously in AIG hospitals, Hyderabad, India, and Gastrodex, Dexeus University Hospital center in Spain. The task layout of the study team members will be as follows:

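### The under-25% excess-weight-loss failure rule sets a hurdle that rises with entry BMI, and the protocol neither defines ideal weight nor plans to account for entry BMI

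*Protocol*

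**What the plan says.** - **Failure rule.** Section 1.3 states: "we define Failure of BE methods when patient only obtain less than 25% of EWL after 6 months of BE". It ties this to the first item of the BAROS scale adapted to endoscopy. This is the only numerical weight criterion that the protocol adopts for itself.
- **Measure.** Table 1, item 1, builds %EWL from "Initial weight – Current weight) / (Initial weight – Ideal weight) × 100". Ideal weight is not defined. The nearest figure is the control-group limit in section 4.2 ("with BMI less than 25"), which is not a definition of ideal weight.
- **Entry.** Section 4.3, inclusion criterion 2, reads "IMC basal ≥ 30 kg/m²". Neither the inclusion nor the exclusion criteria give an upper limit.
- **Target of prediction.** Section 3.1 asks whether EGG parameters "can predict clinical success at the end of follow up". It gives no numerical definition of success.
- **Scale used elsewhere.** The Summary and sections 1.1 and 1.3 describe response as total body weight loss (TBWL). Section 1.1, for example, aims to "increase the likelihood of successful total body weight loss (TBWL) and maintenance". No cut is given on that scale.
- **Analysis.** Section 5 says "The possibility of multivariate logistic regression analysis will be explored" and names no covariate.

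**The concern.** The %EWL denominator is the weight above ideal, which is a larger share of body weight in a heavier patient. A single 25% cut is therefore a different demand, as a percentage of body weight, at each entry BMI. Two patients who lose the same proportion of their weight can receive opposite labels because they started at different BMIs.

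The study wants to know whether EGG and water-load findings predict individual outcome, and its secondary objective is to match patients to procedures. If a marker is related to entry BMI, or if procedure groups differ in entry BMI, an association with failure could come partly from how the label is built and not from gastric physiology.

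**Working it through.** The plan has no figure of its own to reproduce, so the check starts from its formula.

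**1. The hurdle.** At fixed height, weight is proportional to BMI. Let B be entry BMI and I the BMI that corresponds to ideal weight. Losing 25% of excess weight means losing 0.25 × (B − I) BMI units. As a percentage of body weight:

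%TBWL needed = 25 × (B − I) / B

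This rises with B for any I above zero, so the direction needs no assumption. The size depends on I, which is assumed here:

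| Ideal BMI (assumed) | B = 30 | B = 40 | B = 50 | Ratio 50:30 |
|---|---|---|---|---|
| 25 | 4.17% | 9.38% | 12.5% | 3.0 |
| 22 | 6.67% | 11.25% | 14.0% | 2.1 |
| 21 | 7.5% | 11.88% | 14.5% | 1.9 |

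Example of the first row: 25 × 5/30 = 4.17 and 25 × 25/50 = 12.5. BMI 50 is an illustrative extreme. For BMI 40 against 30 the ratio is 1.7 to 2.3 (ideal BMI 22 to 25).

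**2. Same loss, different label.** With ideal BMI 25, an 8% loss is 8 × 35/10 = 28% EWL at BMI 35 (not failure) and 8 × 40/15 = 21% EWL at BMI 40 (failure). With ideal BMI 22 both are failures (8 × 35/13 = 21.5% and 8 × 40/18 = 17.8%), so this example depends on the reference chosen.

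**3. Failure rate by entry BMI.** Assume %TBWL is normal with mean 12 and SD 6 at every BMI. The probability of falling below the hurdle is:

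| Ideal BMI | BMI 32 | BMI 35 | BMI 40 | BMI 45 |
|---|---|---|---|---|
| 25 | 14% | 21% | 33% | 44% |
| 22 | 24% | 33% | 45% | 55% |

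**4. A marker with no real predictive value.** Assume entry BMI with mean 37 and SD 5, limited to 30-55. The marker is correlated with BMI but unrelated to weight loss, and %TBWL is as in step 3. Failure in the upper v lower half of the marker, with ideal BMI 25, is 29% v 24% at correlation 0.3 and 30% v 22% at correlation 0.5. With ideal BMI 22 it is 40% v 35% and 42% v 33%.

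A second set of assumptions (BMI mean 38, SD 5, values below 30 set to 30; %TBWL mean 15, SD 8) gives an AUC of 0.53-0.54 at correlation 0.3 and 0.55-0.56 at 0.5. In a group of 50, a nominal 5% rank test rejects about 6% and 8-9% of the time. With zero correlation the AUC is 0.50 and the rejection rate about 4.5%.

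**5. Procedure groups.** If two groups had mean entry BMI 34 and 42 (assumed, SD 4) and the same %TBWL distribution as in step 3, failure would be 19% v 37% (ideal BMI 25) or 30% v 49% (ideal BMI 22).

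**6. Dropping the independence assumption.** Let mean %TBWL be 12 + 0.4 × (B − 37), SD 6, ideal BMI 25. EWL failure at BMI 32, 35, 40 and 45 is then 22%, 25%, 26% and 25%, which is nearly flat. A fixed 8% TBWL cut under the same model gives P(%TBWL < 8) of 37%, 30%, 19% and 12%. In that case the TBWL cut is the label that depends on BMI.

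**The case against.** The strongest objection is that a rising hurdle is not the same as a rising failure rate. Steps 3 to 5 assume that proportional loss is unrelated to entry BMI, and nothing in the protocol supports that. Step 6 shows that a moderate positive slope removes the gradient in the EWL label and moves the BMI dependence to a fixed TBWL cut. This stands. It rules out the inference that %EWL must be replaced by a TBWL responder cut, and the 25% line is in any case a pre-stated band of a named scale.

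Other limits also stand:

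- A reader might infer that the rule demands three times as much from a BMI 50 patient. That holds only for ideal BMI 25, which the protocol does not state.
- A reader might infer that EGG findings will look predictive because they track BMI. The protocol shows no such link among obese patients, and section 1.3 calls their pattern unknown. The non-obese controls do not imply one: section 6 says they are there to establish the normal pattern.
- The rule covers endoscopic methods at 6 months. Reading success at the end of follow-up as its complement, or applying it to the surgical groups, is inference.

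It can also be said that covariates may be left to an analysis plan. That answers the adjustment in part, but the label and its undefined reference weight are fixed in this protocol.

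**Conclusion.** The point holds in a limited form. The hurdle rises with entry BMI under the protocol's own formula, whatever ideal weight is used. Over ideal BMI 21 to 25, a BMI 50 patient needs 1.9 to 3.0 times the proportional loss of a BMI 30 patient. Whether this distorts the EGG results depends on two things the protocol does not establish: a relation between marker and BMI among obese patients (or a difference in entry BMI between procedure groups), and how proportional loss varies with BMI. At assumed correlations of 0.3 to 0.5, with loss independent of BMI, the spurious signal for a single marker is modest. It could be larger where groups with different entry BMI are compared. The change is worth making because it is nearly free and protects the analysis whichever way the dependence on BMI runs.

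**What to change.** 1. Keep the BAROS failure label of under 25% EWL, and state the ideal-weight reference used to compute it.
2. Add percent total body weight loss, (initial − current)/initial × 100, as a continuous outcome beside the label. No TBWL cut is needed.
3. State that analyses relating EGG and water-load measures to outcome, and comparisons between procedures, are adjusted for entry BMI.

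Weight and BMI are already collected (section 4.4), so no new measurement is needed. The cost is one covariate in groups of 50 and a little extra analysis. Comparability with BAROS-based reports is kept.

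### The under-25% EWL failure rule is likely to leave too few failures for a success/failure analysis within each procedure; continuous weight loss should be the main outcome of the EGG prediction analysis

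*Protocol*

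**What the plan says.** Section 1.3 sets the rule for this protocol: "we define Failure of BE methods when patient only obtain less than 25% of EWL after 6 months of BE". It takes the rule from part 1 of the BAROS scale as adapted to endoscopic treatment. Table 1 also prints a graded %EWL score and total-score bands, but the text adopts neither as the study outcome.

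The protocol's expectations for weight loss are:

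- **ESG**, at the same 6-month time point: "patients after ESG at 6 months achieved a mean of 50% of EWL or more" (section 1.3).
- **Gastric bypass**: "allowing average weight loss of around 30%, without side effects of intestinal malabsorption" (section 1.2), with no scale or time point.
- **Sleeve gastrectomy**: "results close to those of gastric bypass" (section 1.2), with no figure of its own.
- **Balloon**: no %EWL figure.

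Section 4.2 plans 50 patients per procedure and calls the study a pilot. The primary objective (section 3.1) is to predict, from EGG parameters, clinical success when follow-up ends, and also adverse events. Section 5 commits to group comparisons and to Pearson or Spearman correlations whose variables are not named. Of modelling it says: "The possibility of multivariate logistic regression analysis will be explored".

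**The concern.** The cut lies well into the lower tail of the outcome that the protocol itself expects after ESG. A dichotomy placed there puts few patients in the failure class and treats everyone above 25% EWL as alike, although weight is measured on a continuous scale.

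Predicting success means relating an EGG parameter to outcome. The secondary objective, choosing a procedure from the pre-intervention EGG, needs that relation within each procedure. With a handful of failures among 50 patients the EGG effect is poorly estimated, and a model with several covariates cannot be supported. A null result would then be hard to interpret.

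**Working it through.** The protocol states no SD, expected failure rate, power or sample-size calculation, so there is no figure of its own to reproduce.

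**Inputs from the protocol:** cut 25% EWL; ESG mean 50% or more at 6 months; bypass about 30%; 50 per group.

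**Assumptions:** %EWL normal; SD 20-30 points (15 shown for comparison); ideal weight at BMI 25; the bypass 30% read as total body weight loss (TBWL); baseline BMI 35-50 in the surgical groups; no dropout; two-sided alpha 0.05.

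**1. Expected ESG failures** = 50 × Φ((25 − mean)/SD).

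| Mean EWL | SD 15 | SD 20 | SD 25 | SD 30 |
|---|---|---|---|---|
| 50% | 2.4 | 5.3 | 7.9 | 10.1 |
| 60% | 0.5 | 2.0 | 4.0 | 6.1 |

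For example, at mean 50 and SD 20: Φ(−1.25) = 0.106, and 50 × 0.106 = 5.3. At mean 50 and SD 20-30 the failure rate is 11-20%. The chance of no ESG failure at all is 0.4% at SD 20 and 9% at SD 15.

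**2. Sleeve and bypass, if the rule were applied to them.** Mean EWL = TBWL × BMI/(BMI − 25). At 30% TBWL this is 105%, 80%, 67.5% and 60% at BMI 35, 40, 45 and 50. Put the other way, the cut of 25% EWL equals a TBWL of 25 × (BMI − 25)/BMI = 7.1%, 9.4%, 11.1% and 12.5%.

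- With a TBWL SD of 6-12 points, expected failures are 0.0-3.6 of 50.
- With an EWL SD of 20-30 points instead, they are 0.1-1.7 at BMI 40, 0.8-3.9 at BMI 45 and 2.0-6.1 at BMI 50.
- If the loss were 20% TBWL, the two SD models together give about 1-15 of 50.

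**3. Information kept by the cut**, relative to continuous weight loss, is φ(z)²/(p(1 − p)).

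- p = 0.106 (z = −1.25): 0.1826²/(0.1056 × 0.8944) = 0.35.
- p = 0.202 (z = −0.83): 0.2819²/(0.2023 × 0.7977) = 0.49.

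So half or more of the information is discarded.

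**4. Power within one group of 50, true correlation 0.3** (20,000 simulations per setting).

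- Continuous weight loss: about 57%. The Fisher z approximation gives Φ(0.3095 × √47 − 1.96) = Φ(0.16) = 56%.
- Cut at 11-20% failures: about 23-32%, comparing the mean EGG parameter between failures and successes.

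**5. Power by number of failures**, for a 0.8 SD difference in an EGG parameter: Φ(0.8/√(1/k + 1/(50 − k)) − 1.96) for k failures gives 20%, 40%, 55% and 62% at k = 2, 5, 8 and 10.

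**The case against.** Several points on the other side are sound.

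- **Scope of the rule.** It is worded for endoscopic methods at 6 months, while the primary objective concerns success when follow-up ends, at 12 months, and covers surgery too. Applying it to sleeve and bypass is an inference. This stands, so the surgical figures are conditional.
- **Few or no failures.** A reader might infer that the protocol's own figures leave almost no failures in all three groups. They do not show this. No SD, mean baseline BMI or ideal-weight rule is given, the 30% has no scale or time point, and 5-10 ESG failures is neither none nor nearly none.
- **The primary objective cannot be met.** A reader might infer this as well, but it does not follow. The balloon group, for which no %EWL is given, may supply failures. The primary objective is not stated per procedure, and with 20-30 failures among 200 pooled patients power for a 0.8 SD difference would be 92-98%. Pooling needs adjustment, because failures would cluster in the less effective procedures and mix EGG with procedure. The adverse-event objective does not depend on the cut.
- **Logistic regression as the only analysis.** Correlations are a firm commitment and logistic regression is only to be explored. Correlating EGG with continuous weight loss is open under section 5. But the variables are not named, so the protocol does not commit to it.
- **Pilot status and choice of model.** Within one group of 50, power is only about 57% at a correlation of 0.3 even with the continuous outcome, so a null result could not be blamed on the cut alone. The form of the model can be left to an analysis plan, and success or failure is a legitimate responder question. However, the protocol itself fixes the cut, and keeping it as a secondary class preserves that question.

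**Conclusion.** The narrower point holds. A success/failure analysis at under 25% EWL within ESG, and within sleeve or bypass if the rule is extended to them, is likely to have too few failures and would discard half or more of the information in measured weight loss.

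The ESG part is the firmer one. It uses a mean and a cut from the same section at the same time point, and needs only normality and an SD. The surgical part is less certain, since it also depends on the scale and timing of the 30%, baseline BMI and ideal weight. Nothing is claimed for the balloon group.

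Should-fix, moderate confidence.

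**What to change.** In section 5:

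1. Make continuous weight loss (%TBWL, with continuous %EWL alongside) the main outcome of the EGG prediction analysis, at the visit that defines clinical success, and state that visit for all four groups.
2. Use linear regression of weight loss on the EGG parameter, by procedure or with procedure in the model.
3. Name weight loss as a variable in the correlations already planned.
4. Keep under 25% EWL as a secondary classification and report the number of failures per group.

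The cost is wording only, since section 4.4 already collects weight. The headline result becomes a slope rather than a success rate, and power within one group of 50 stays modest: 56% at a correlation of 0.3 and 83% at 0.4 by the Fisher z approximation.
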